6.2.7 Safety Events

All safety events in this study will be listed.

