## **5.4 Safety**

The primary and secondary efficacy outcomes and measures serve as the primary and secondary safety outcomes and measures. Other safety outcome measures include other serious adverse events resulting in hospitalization or emergency visits.

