### **5.4.2 Severe Adverse Events Collection Reports**

In addition to the primary and secondary outcome events, the present study also collect other severe adverse events resulting in hospitalization or emergency visits, which includes cardiac insufficiency, heart failure; arrhythmias, such as atrial fibrillation, atrial flutter, and supraventricular tachycardia; other thrombotic events, such as pulmonary embolism, deep venous thrombosis; neurological diseases, such as Alzheimer's disease, dizziness and vertigo (excluding stroke), tumors; respiratory system diseases, such as pulmonary infection, acute onset of COPD; digestive system diseases, such as gastrointestinal bleeding, tumors; urinary system diseases, such as renal insufficiency, hemodialysis, urinary tract infections, tumors; endocrine system diseases, such as diabetes, tumors; hematological system diseases, such as anemia, tumors; musculoskeletal system diseases, such as fractures, cervical and lumbar diseases, tumors; other unclassified reasons, such as social factors. Physical examination needs do not fall into this category.

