7.3 Supplementary tables

Table 33 List of safety events

Table 34 List of concomitant medications

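### Other serious events leading to hospitalization or an emergency visit are a stated safety outcome, but the SAP plans only a listing, so no by-arm summary of the non-bleeding events is prespecified

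*SAP*

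**What the plan says.** Protocol 5.4 first lets the primary and secondary efficacy outcomes double as the primary and secondary safety outcomes. It then adds a separate item: "Other safety outcome measures include other serious adverse events resulting in hospitalization or emergency visits".

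Protocol 5.4.2 sets out what is collected under that item, by body system. The categories include:
- cardiac: "cardiac insufficiency, heart failure; arrhythmias, such as atrial fibrillation, atrial flutter, and supraventricular tachycardia";
- thromboembolic: "other thrombotic events, such as pulmonary embolism, deep venous thrombosis";
- renal and urinary: "urinary system diseases, such as renal insufficiency, hemodialysis, urinary tract infections, tumors";
- digestive: "digestive system diseases, such as gastrointestinal bleeding, tumors".

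For analysis, SAP 6.2.7 consists of one sentence: "All safety events in this study will be listed". The matching output, in SAP 7.3, is "Table 33 List of safety events", given as a title without a shell.

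**The concern.** An outcome measure that the protocol names should have a planned summary by randomised group. Followed as written, the SAP gives this one a line listing, which carries no denominators and no contrast between arms.

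Apart from bleeding, this item is the only safety information that is separate from the efficacy endpoints. None of MACE-3, MACE-4 or MACE-5 contains heart failure, arrhythmia or venous thromboembolism, so these events are not summarised by arm under another heading. If no summary is fixed in advance, the choice of what to count, how to group it and whether to show it by arm is made with the data in view.

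**Working it through.** **Step 1. Compare the planned treatment of neighbouring items.**

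| Item | SAP method | By-arm table | Listing |
|---|---|---|---|
| MACE composites and components | Kaplan-Meier, log-rank, Cox (6.2.3, 6.2.4) | Tables 5 to 10 | none |
| Laboratory results | descriptive by group (6.2.5) | Table 14 | none |
| Bleeding (cerebral, massive gastrointestinal) | descriptive (6.2.6) | Table 16, with a P column | none separate |
| Concomitant medications | listed (6.2.8) | Table 15, with a P column | Table 34 |
| Other serious events | listed (6.2.7) | none | Table 33 |

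Other serious events are the only row without a by-arm table. Concomitant medications are the closest comparison: their method sentence is also a promise to list, yet a by-arm shell is supplied as well.

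**Step 2. Check whether general text fills the gap.** Protocol 9.2.1 has a general sentence promising summary statistics by DACAB group, and SAP 6.2.1 provides counts and percentages for discrete variables. Neither mentions safety events. Protocol 9.2.1 leaves the detailed methods to the SAP, and the specific SAP rule is a listing.

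**Step 3. Estimate how precise a by-arm table would be.** The documents state no power or precision figure for these events, so there is none to reproduce.

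- Arm sizes (Protocol 9.3 and SAP 6.3): T+A 168, T 166, A 166; 168 + 166 + 166 = 500.
- Event rate: not given. The 5-year rates below are assumptions.
- Half-width of the 95% CI for T+A versus A at a common rate p: 1.96 × √[p(1 − p)(1/168 + 1/166)], where √(1/168 + 1/166) = 0.1094.
- Example at p = 10%: 1.96 × 0.300 × 0.1094 = 0.064.

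| Assumed rate, both arms | Expected subjects with an event, arm of 166 | 95% CI half-width (points) | Higher rate detectable with 80% power, two-sided 5% |
|---|---|---|---|
| 5% | 8.3 | 4.7 | 14.0% |
| 10% | 16.6 | 6.4 | 21.1% |
| 20% | 33.2 | 8.6 | 33.6% |
| 30% | 49.8 | 9.8 | 44.8% |

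**Step 4. Test a doubling.** At 20% in T+A and 10% in A, the half-width is 1.96 × √(0.2 × 0.8/168 + 0.1 × 0.9/166) = 7.6 points. An observed 10-point difference would exclude zero, but the power to detect a true doubling is only about 73%.

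For a single category the rate is likely to be lower. At an assumed 3%, about 5 subjects per arm have an event (166 × 0.03 = 5.0), and the power for a doubling to 6% is about 26%. At 2% against 4% it is about 19%.

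**The case against.** The strongest reply is that this is a lower-tier outcome and the gap is one of presentation.

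- **The main safety outcomes are analysed.** The efficacy endpoints that serve as primary and secondary safety outcomes have full time-to-event analyses by arm, and the two major bleeding types have Table 16. This stands, and it limits the weight of the point.
- **Listing need not exclude a summary.** The SAP says it will list concomitant medications and still tabulates them by arm. Table 33 has no shell, and arm assignment is known for every subject. A reader might infer from the plan that the trial will have no by-arm result for these events, or that a difference between regimens cannot be seen. The documents do not support that: counts could be derived afterwards. They support only that none is prespecified.
- **The data are softer.** The events are gathered at one visit about 5 years after surgery. They are not among those that Protocol 7.3 names for adjudication by the endpoint committee, and 5.4.2 mixes heart failure with dizziness, fractures and social reasons. This stands, and it is a reason to keep the table descriptive.
- **Contrasts in single categories will be weak.** This also stands, as step 4 shows. A reader might expect the arm sizes to establish a doubling from 10% to 20%; 73% power does not justify that.
- **Cohort comparisons are outside the plan.** A reader might also want the table repeated by 1-year graft status. Protocol 2.3 and SAP section 2 limit those comparisons to nine named endpoints, none of which is an event of this kind. Leaving heart failure out of the composites is likewise an endpoint choice and not an error in the plan.

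None of this supplies the missing by-arm summary.

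**Conclusion.** The point holds in a limited form. The protocol states the outcome and collects it by category, while the SAP sets a method that, followed literally, gives no by-arm summary of the non-bleeding events. This is more than missing detail, because the specific SAP rule is a listing and the general sentences do not override it.

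The consequence is modest. The primary analysis, the MACE components and the two bleeding types in Table 16 are unaffected. What is lost is a prespecified by-arm description of events such as heart failure, arrhythmia, venous thromboembolism and renal insufficiency. Such a description would carry a 95% CI half-width of roughly 4.7 to 9.8 points over assumed rates of 5% to 30%. That range rests on assumed rates, equal rates in the two arms, the normal approximation, and all randomised subjects counting in the denominator. Rare categories will be imprecise.

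**What to change.** Change SAP 6.2.7 so that, besides the listing, it calls for one descriptive table in the format of Table 16, with these contents:
- per randomised arm, the number and percentage of subjects with at least one such event (hospitalization or emergency visit), with the denominator stated;
- one overall row and one row per Protocol 5.4.2 category, with heart failure in its own row;
- 95% CIs for the between-arm differences in place of the P column.

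Keep Table 33 as the supporting listing. A repeat by 1-year graft cohort is optional. If it is added, label it as outside the stated exploratory objectives.

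The cost is a sentence or two of SAP text and one table shell; no new data are needed. The downside is a further set of descriptive comparisons, on events not named for adjudication and with few subjects in many rows. Report them without significance claims and state these limits in a footnote.

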6.2.8 Concomitant medications

All concomitant medications in this study will be listed.

6.2.9 Graft vessels cohorts

According to the imaging examination results of graft vessels at 1 year after surgery, all subjects were divided into two natural cohorts with or without graft failure. First, baseline characteristics will be compared between the two cohorts. χ^2 test or Fisher's exact probability method are used to compare dichotomous data, CMH χ^2 test is used to compare polytomous data; t test, ANOVA or non-parametric test are used to compare continuous data. Then, GLM method will be used to compare different outcomes after adjusting for potential confounding factors.

The outcomes of two cohorts with or without vein graft failure will be analyzed similarly with the graft failure cohort.

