4.1 Primary Outcome

MACE-4, defined as a composite of all-cause death, myocardial infarction, stroke, and coronary revascularization. The outcome measure is the time to the first occurrence of MACE-4 event from randomization to the last visit.

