4.3 Evaluation and Calculation of Endpoints

The primary outcome is the time to the first occurrence of any MACE-4, which is a composite of all-cause death, myocardial infarction, stroke, and coronary revascularization and measured in days since the date of randomization. Subjects who had not experienced any major adverse clinical events from randomization to the last visit will be right-censored. For those subjects who lost to follow-up at 5-year visit, the date of the last contact and the most updated clinical outcomes available in medical record or other source will be used in primary analysis. If there's no major adverse clinical events recorded for those subjects who lost to follow-up at 5-year visit, then these subjects will be right-censored at the date of their last contact. The survival curves will be estimated using Kaplan-Meier method.

The secondary outcomes (time to event) will be analyzed similarly with the primary observational endpoint.

Graft failure after CABG is in accordance with Fitzgibbon classification criteria by using MSCTA or CAG, there were a total of 3 categories, grade A, B and O, where grade A accounted for graft patency (no lesions), and grade B/O accounted for the graft failure.

5. Subject Selection Criteria

All the subjects enrolled in the DACAB trial.

6. Statistical Analysis

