7.1.2 Primary Outcome

Table 5 Occurrence of MACE4 during follow-up (FAS)

Group	Overall occurrence of the event	Event rate during follow-up				
		12 months	24 months	36 months	48 months	60 months
A	*** (***)	**%	**%	**%	**%	**%
T+A	*** (***)	**%	**%	**%	**%	**%
T	*** (***)	**%	**%	**%	**%	**%

Note: Overall occurrence of the event includes all the events during the follow-up period, KM was used to estimate the event rates in different visit.

Table 6 Survival Analysis for MACE4 event during follow-up (FAS)

Group	HR(95% CI)	Logrank P
T+A VS. A	*** (***, ***)	0. ****
T VS. A	*** (***, ***)	0. ****
T+A VS. T	*** (***, ***)	0. ****

Figure 1. Kaplan-Meier curves of MACE4 during the follow-up (FAS)

Table 7 Occurrence of MACE4 during follow-up (PP)

Group	Overall occurrence of the event	Event rate during follow-up				
		12 months	24 months	36 months	48 months	60 months
A	*** (***)	**%	**%	**%	**%	**%
T+A	*** (***)	**%	**%	**%	**%	**%
T	*** (***)	**%	**%	**%	**%	**%

Note: Overall occurrence of the event includes all the events during the follow-up period, KM was used to estimate the event rates in different visit.

Table 8 Survival Analysis for MACE4 event during follow-up (PP)

Group	HR(95% CI)	Logrank P
T+A VS. A	*** (***,***)	0. ****
T VS. A	*** (***,***)	0. ****
T+A VS. T	*** (***,***)	0. ****

Figure 2. Kaplan-Meier curves of MACE4 during the follow-up (PP)

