7.2.2 Major clinical events

Table 28 Occurrence of clinical events during the follow-up (grouped by total grafts failure at 1 year)

Indicator/Group	Overall occurrence of the event	Event rate 2-5 years during follow-up			
		24 months	36 months	48 months	60 months
MACE4					
Patency	*** (***)	**%	**%	**%	**%
Failure	*** (***)	**%	**%	**%	**%
MACE5					
Patency	*** (***)	**%	**%	**%	**%
Failure	*** (***)	**%	**%	**%	**%
MACE3					
Patency	*** (***)	**%	**%	**%	**%
Failure	*** (***)	**%	**%	**%	**%
All-cause death					
Patency	*** (***)	**%	**%	**%	**%
Failure	*** (***)	**%	**%	**%	**%
Cardiovascular death					
Patency	*** (***)	**%	**%	**%	**%
Failure	*** (***)	**%	**%	**%	**%

Event rate 2-5 years during follow-up

Indicator/Group	Overall occurrence of the event	24 months	36 months	48 months	60 months
Myocardial infarction					
Patency	*** (***)	**%	**%	**%	**%
Failure	*** (***)	**%	**%	**%	**%
Non-silent MI					
Patency	*** (***)	**%	**%	**%	**%
Failure	*** (***)	**%	**%	**%	**%
Stroke					
Patency	*** (***)	**%	**%	**%	**%
Failure	*** (***)	**%	**%	**%	**%
Coronary revascularization					
Patency	*** (***)	**%	**%	**%	**%
Failure	*** (***)	**%	**%	**%	**%

Table 29 Survival analysis for clinical events (grouped by total grafts failure at 1 year)

Indicator/Group	HR(95% CI)	Adjusted P
MACE4		
Failure VS. Patency	*** (***, ***)	0. ****
MACE5		
Failure VS. Patency	*** (***, ***)	0. ****
MACE3		
Failure VS. Patency	*** (***, ***)	0. ****
All-cause death		
Failure VS. Patency	*** (***, ***)	0. ****
Cardiovascular death		
Failure VS. Patency	*** (***, ***)	0. ****
Myocardial infarction		
Failure VS. Patency	*** (***, ***)	0. ****
Non-silent MI		
Failure VS. Patency	*** (***, ***)	0. ****
Stroke		
Failure VS. Patency	*** (***, ***)	0. ****
Coronary revascularization		
Failure VS. Patency	*** (***, ***)	0. ****

Table 30 Occurrence of clinical events (grouped by saphenous vein grafts failure at 1 year)

Note: same as table 28, grouped only according to saphenous vein grafts failure at 1 year.

Table 31 Survival analysis for clinical events (grouped by saphenous vein grafts failure at 1 year)

Note: same as table 29, grouped only according to saphenous vein grafts failure at 1 year.

Table 32 Grafts patency during 1-5 years follow-up

Indicator	Overall	Patency (A)	Failure (O/B)	Adjusted P
Total grafts at 1 year				0.***
N(missing)	*** (***)	*** (***)	*** (***)	

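### SAP 6.2.9 compares cohorts defined by 1-year imaging without a landmark, a risk set or a rule for non-fatal events before the scan, and leaves the model behind Table 29's hazard ratios unspecified

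*SAP*

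**What the plan says.** SAP 6.2.9 uses the 1-year graft images so that "all subjects were divided into two natural cohorts with or without graft failure", and treats vein graft failure in the same way. After a comparison of baseline characteristics, "GLM method will be used to compare different outcomes after adjusting for potential confounding factors". The section gives no time origin, family, link or covariate list.

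The time-to-event definitions stand elsewhere. SAP 4.1 states: "The outcome measure is the time to the first occurrence of MACE-4 event from randomization to the last visit". SAP 4.3 adds that the primary outcome is "measured in days since the date of randomization". SAP 4.2 and protocol sections 5.3 and 8.1 use the same origin.

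The table shells in SAP 7.2.2 point to a later window. Table 28 is headed "Event rate 2-5 years during follow-up" and has columns at 24, 36, 48 and 60 months but none at 12. Another shell is titled "Table 32 Grafts patency during 1-5 years follow-up". The shell "Table 29 Survival analysis for clinical events (grouped by total grafts failure at 1 year" reports a hazard ratio with 95% CI, and only its P column is labelled as adjusted. Table 28 also has an overall-occurrence column. The note to Table 5 explains a column of the same title: "Overall occurrence of the event includes all the events during the follow-up period".

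**The concern.** The exploratory question is whether graft failure seen at 1 year goes with later clinical events. Cohort membership is known only at the scan. An MI, stroke, revascularisation or unstable-angina admission before the scan cannot be a consequence of a status established later, and it may be what revealed the failed graft. A programmer who applies SAP 4.1 to 4.3 literally would count such events and still comply with the SAP.

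If early events cluster in the failure cohort, the association is overstated. If they cluster in the patent cohort, it is understated. This concerns MACE-3, MACE-4, MACE-5 and the non-fatal components. Death is little affected, because a subject must survive to be imaged.

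The second gap is the model. Without a family and link, a reader cannot tell what the Table 29 estimate is, and must infer that it is adjusted. The SAP is dated 5 June 2021 and the protocol timetable puts database lock in June 2021, so these choices may be settled with data in hand.

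**Working it through.** The plan gives no event count, power or hazard ratio for this comparison, so there is no figure to reproduce.

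**1. Are there early events?** SAP 1 gives 1-year MACE of 1.8%, 2.4% and 5.4% in arms of 168, 166 and 166.
- 168 × 0.018 = 3.0; 166 × 0.024 = 4.0; 166 × 0.054 = 9.0; total 16.
- SAP 6.3 gives 5 deaths before the 12-month visit. If all 5 are among the 16, 16 − 5 = 11 are non-fatal. If none are, up to 16 are.
- Both counts assume that the parent trial's MACE, which these documents do not define, matches MACE-4.

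**2. Illustration of the bias.** Stated input: N = 500 − 5 = 495 subjects (protocol 9.3). Assumed inputs: all 495 are imaged, a fraction f is in the failure cohort, 5-year risk is R, E early events occur at 0.5 years on average, and a share s of them falls in the failure cohort. Both cohorts have the same hazard after month 12 (true HR 1).
- Post-scan risk p = (R·N − E)/(N − E); hazard h = −ln(1 − p)/4; expected post-scan time per event-free subject = p/h.
- Example, f = 0.3, R = 0.2, E = 11, s = 0.7: p = (99 − 11)/484 = 0.1818, h = 0.0502, p/h = 3.624 years.
- Failure cohort (148.5 subjects, 7.7 early events): events 7.7 + 140.8 × 0.1818 = 33.3; person-years 7.7 × 0.5 + 140.8 × 4.624 = 654.9; rate 0.0508.
- Patent cohort (346.5 subjects, 3.3 early events): events 3.3 + 343.2 × 0.1818 = 65.7; person-years 3.3 × 0.5 + 343.2 × 4.624 = 1,588.7; rate 0.0414.
- Ratio = 1.23, although the true post-scan HR is 1.

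Crude ratio on the randomisation clock, f = 0.3, E = 11:

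| Share of early events in failure cohort | R = 20% | R = 30% |
|---|---|---|
| 20% | 0.95 | 0.97 |
| 30% (proportional) | 1.00 | 1.00 |
| 50% | 1.11 | 1.07 |
| 70% | 1.23 | 1.15 |

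With f from 0.2 to 0.4 and s from 20% to 70%, the range is 0.91 to 1.39 for E = 11 and 0.87 to 1.60 for E = 16. Neither range is a bound.

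An unadjusted Cox simulation (3,000 runs per cell, f = 0.3, E = 11) agrees: 0.94–0.96, 1.00, 1.07–1.10 and 1.15–1.22 for the four shares. The false-positive rate is about 8% at a 50% share and 13–16% at 70%, against a nominal 5%. Starting at the scan and excluding prior events gives HR 0.98–1.00 with 4.6–5.3% false positives.

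**3. Sampling error.** The 95% margin on the HR is exp(1.96/√(D × 0.3 × 0.7)). With D = 0.2 × 495 = 99 events it is a factor of 1.54; with D = 0.3 × 495 = 148.5 it is 1.42. The largest main-scenario shift, 1.23, lies inside it.

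**4. Does the choice of model change the number?** With reference risk p0 and HR 2.0, p1 = 1 − (1 − p0)².
- p0 = 0.20: p1 = 0.36, risk ratio 1.80, odds ratio 2.25.
- p0 = 0.30: p1 = 0.51, risk ratio 1.70, odds ratio 2.43.

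A binary GLM would therefore not return the HR that Table 29 promises.

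**The case against.** The best reply is that the shells already intend a post-year-1 analysis. Tables 5, 7 and 9 have a 12-month column and Table 28 drops it under a header for years 2 to 5, while SAP 4.1 to 4.3 define the primary and secondary outcomes, not the exploratory cohorts. This has weight. A reader might infer that the plan deliberately counts pre-scan events; the documents do not support that. What stands is that a header sets neither an origin nor an event rule, that the overall-occurrence column carries a title defined elsewhere as covering all follow-up, and that Table 29 states no window.

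A reader might also infer that a GLM cannot produce a hazard ratio. That goes too far: piecewise Poisson and complementary log-log models can. The fault is that the model is unspecified. Likewise, 6.2.9 speaks of adjustment and Table 29 shows an adjusted P, so its HR is probably adjusted; it is simply not labelled so.

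A third tempting reading is that waiting to be imaged distorts the mortality comparison. If all cohort members are alive at a common scan time, moving the origin by a common 12 months leaves the Cox HR unchanged. Kaplan-Meier rates do still depend on the origin.

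Finally, the sizes rest on inputs that the documents do not give. That is correct, and they are an illustration only.

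**Conclusion.** The gap is real and of modest weight. The plan does not fix the landmark, the risk set, the handling of earlier non-fatal events or the model for the graft-failure cohorts, and its one written clock would let outcomes precede the exposure.

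The direction of any bias depends on where the early events fall, and in the illustration it vanishes if they split in proportion to cohort size. In the main scenario the shift is smaller than sampling error; it becomes larger with a small failure cohort and more early events. All of this assumes a failure proportion, a 5-year risk, an early-event share and complete imaging, and it equates the parent trial's MACE with MACE-4.

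The analysis is exploratory and non-randomised. Nothing here touches the randomised primary comparison. It is a cheap improvement.

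**What to change.** In SAP 6.2.9:
- **Landmark.** Use either a fixed 12 months or the date of the protocol-scheduled 1-year scan. State which scans qualify, so that a symptom-driven scan does not set the start.
- **Risk set.** Include only subjects alive, under follow-up and with a qualifying image.
- **Events.** For each outcome, count only events after the landmark and exclude subjects who already had that outcome. As a sensitivity analysis, keep them and adjust for the prior event.
- **Tables 28 to 31.** Apply these rules throughout, including the overall-occurrence column. Either keep the 24-to-60-month columns as months since CABG or randomisation, conditional on the landmark, or renumber them 12 to 48 months since the landmark. Merely relabelling the present columns as time since the scan would not work: the last visit is 5 years ± 3 months after CABG, so observation ends about 45 to 51 months after a 12-month scan.
- **Model.** Replace the GLM by a Cox model for Tables 29 and 31, adjusted for randomised arm and a short, named set of baseline covariates, and label the HR as adjusted.

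The work is SAP wording, table notes and re-derived start dates from data already held. Early events and unimaged subjects leave the analysis. On the assumed inputs, dropping 11 events raises the standard error by √(99/88) = 1.06 or √(148.5/137.5) = 1.04, that is 4–6%, before any loss of unimaged subjects, whose number the documents do not give. The result then applies only to imaged 1-year survivors.
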